#### 5.3.3.2 Rave Specimen Tracking Process Steps

**Step 1:** Complete the **Histology and Disease** form (but do not upload reports until a specimen label can be applied to them) and the Baseline forms regarding **Prior Therapies**. Enter the initial clinical specimen data:

- **Specimen Tracking Enrollment** CRF: Enter Time Point, Specimen Category, Specimen Type, Block number, Tissue type, Surgical Path ID, and number of labels needed (include extra labels to apply to reports to be uploaded). CRF generates unique Specimen ID.

**Step 2:** Print labels using report in EDC and collect specimen.

- Label specimen containers and write collection date on each label.
- After collection, store labeled specimens as described in Section 5.4.2.
- Apply an extra specimen label to *each* report before scanning. Return to the **Histology and Disease** form to upload any initial Pathology, Radiology, Molecular Reports (up to 4), Surgical (or Operative) reports and Pathology Verification form (when applicable). Return to **Specimen Tracking Enrollment** CRF to upload any molecular report (one per specimen) and/or specimen specific pathology or related report (one per specimen). Uploaded reports should have protected health information (PHI) data, like name, mailing address, medical record number or social security number (SSN), redacted. Do not redact SPID, block number or relevant dates, and include the UPID and patient study ID on each document.

**Step 3:** Complete specimen data entry.

- **Specimen Transmittal** Form: Enter collection date and time and other required specimen details.

**Step 4:** When ready to ship, enter shipment information.

- **Shipping Status** CRF: Enter tracking number, your contact information, recipient, number of containers and ship date once for the first specimen in a shipment.
- **Copy Shipping** CRF: Select additional specimens to add to an existing shipment referenced by the tracking number.

**Step 5:** Print shipping list report and prepare to ship.

- Print two copies of the shipping list, one to provide in the box, the other for your own records.
- Print pathology or other required reports to include in the box. Be sure the printed copy includes the specimen label.

**Step 6:** Send email notification.

- For only one of the specimens in the shipment, click “Send Email Alert” checkbox on the **Shipping Status** CRF to email recipient.

**Step 7:** Ship the specimen(s).

## 5.4 Specimen Collection

### 5.4.1.1 Collection of Bone Marrow Aspirate in Sodium Heparin Tubes for Processing

1. Label EDTA tube(s) according to the instructions in Section 5.4.2.
2. Collect 8-10 mL of bone marrow aspirate in each EDTA (purple top) tube(s).
3. Tubes should be inverted gently at least 3 times.
4. Tubes may be kept at ambient temperature after collection and during shipment

### 5.4.1.2 Collection of Blood in ADC Tubes for Whole Blood Processing

1. Label ADC tubes according to the instructions in Section 5.4.2.
2. Collect up to 10 mL blood in each EDTA tube(s) and gently invert tube to mix.
3. Tubes should be inverted gently at least 3 times.
4. Tubes may be kept at ambient temperature after collection and during shipment

### 5.4.1.3 Collection of Blood for Venetoclax, OATP1B1 biomarker and nivolumab pharmacokinetic studies

1. See Appendix F

## 5.5 Shipping of Specimens from Clinical Site to Other Laboratories

### 5.5.1 Shipping of Specimens to Ohio State CLIA Certified Lab

5.5.1.1 Bone marrow aspirate will be collected and sent as normally for molecular sequencing to Ohio State University sequencing laboratory

### 5.5.2 Shipping of Specimens to Ohio State Leukemia Tissue Bank

5.5.2.1 Specimen Shipping Instructions  
Notify the Leukemia Tissue Bank when patient arrives and orders have been pended.  
The LTB staff will pick up the samples when complete.

5.5.3 Shipping of Specimens to Ohio State Pharmacological Shared Resource (PhASR)

5.5.3.1 See Appendix F

## 5.6 Biomarker Plan

Biomarker Name AND Lab PI and Site	Assay (CLIA: Y/N)	Use (Integral, Integrated, or Exploratory) AND Purpose	Tissue/Body Fluid Tested and Timing of Sample Collection	M/O	Use of NCI Resources (No / Pending Approval / Approved)	Funding Source(s)
Immunophenotyping [name]/The Ohio State University, Director of Flow Cytometry Laboratory [contact]	Multiparameter flow cytometry CLIA: Y No Review Required	Exploratory Depth of Response assessment.	Bone marrow biopsy aspirate - Baseline - End of cycle 1, 2, and 3 Every 3 months starting with cycle 6 - Relapse/EOT	M	ETCTN Biorepository: No CIMAC: No NCLN Genomics Laboratory: No	NO1 correlative funding budget
Cytogenetics [name]/The Ohio State University, Director of Cytogenetics	Karyotype and FISH analyses CLIA: Y No Review Required	Exploratory Depth of Response assessment.	Bone marrow biopsy aspirate - Baseline - End of cycle 1, 2, and 3 Every 3 months starting with cycle 6 - Relapse/EOT	M	ETCTN Biorepository: No CIMAC: No NCLN Genomics Laboratory: No	NO1 correlative funding budget
Global and gene-specific DNA methylation [name](P)/The Ohio State University, Experimental Hematology Lab [contact]	Quantitative DNA methylation with MassARRAY CLIA: N No Review Required	Exploratory To assess global DNA methylation and methylation levels of specific genes involved in immune checkpoint.	Peripheral blood - Baseline - End of each cycle (both induction and maintenance) - Relapse	M	ETCTN Biorepository: No CIMAC: No NCLN Genomics Laboratory: No NCLN PD Laboratory: No	NO1 correlative funding budget

Biomarker Name AND Lab PI and Site	Assay (CLIA: Y/N)	Use (Integral, Integrated, or Exploratory) AND Purpose	Tissue/Body Fluid Tested and Timing of Sample Collection	M/O	Use of NCI Resources (No /Pending Approval/ Approved)	Funding Source(s)
Next generation sequencing AML mutational analysis with Variant Allele Frequency [name] (PI)/ The Ohio State University, Experimental Hematology Lab [contact]	Amplicon Sequencing for 96 gene panel CLIA: N No Review Required	Exploratory Depth of Response assessment.	Bone marrow biopsy aspirate -Baseline -End of cycle 1, 2, and 3 -Every 3 months starting with cycle 6 -Relapse/EOT	M	ETCTN Biorepository: No CIMAC: No NCLN Genomics Laboratory: No NCLN PD Laboratory: No	NO1 correlative funding budget
Tetramer analysis and Cytokine Production up re-stimulation with antigenic peptide [name], PhD (PI)/ The Ohio State University, Experimental Hematology Lab [contact]	Flow cytometry and functional assay CLIA: N No Review Required	Exploratory To identify tumor specific T-cell response to AML cells. These include T cells specific for tumor associated antigen (WT1 and MUC1) as well as T cells recognized tumor specific "neoantigen".	Peripheral blood: -Baseline -After cycles 1, and 3 of induction and cycles 3 and 9 of maintenance Bone marrow biopsy aspirate: -Baseline -End of cycles 1, 2, and 3 -Every 3 months starting with cycle 6 -Relapse/EOT	M	ETCTN Biorepository: No CIMAC: No NCLN Genomics Laboratory: No NCLN PD Laboratory: No	NO1 correlative funding budget
Venetoclax and OATP1B1 biomarker studies [name] PhD/ The Ohio State University, Division of Pharmaceutics and Pharmacology [contact] Nivolumab PK studies [name]/ The Ohio State University, Division of Pharmaceutics	LC/MS-MS and ELISA CLIA: N No Review Required	Exploratory To assess the effect of antifungal agent on venetoclax plasma PK and OATP1B1 plasma biomarker	Peripheral blood -Baseline Cycle 1 (Day 14/15)		ETCTN Biorepository: No CIMAC: No NCLN Genomics Laboratory: No ETCTN Biorepository: No	U24 ChOP-KC U24 ChOP-KC

NCI Protocol #: 10317  
Version Date: 08.16.21

and Pharmacology [contact]	No Review Required	venetoclax/decitabine	- Induction Cycle 2 (Day 1) - Maintenance Cycle 1 (Day 1) - Maintenance Cycle 3 (Day 14) - End of Treatment/Relapse	CIMAC: No Genomics Laboratory: No
---------------------------------------	--------------------	-----------------------	--	---

## 5.7 Integral Laboratory Studies

None

## 5.8 Exploratory/Ancillary Correlative Studies

### 5.8.1 Flow Cytometry

5.8.1.1 Specimen(s) Receipt and Processing at Ohio State University's Leukemia Tissue Bank

5.8.1.2 Site(s) Performing Correlative Study

This exploratory biomarker will be performed locally at the participating institution, then the immunophenotyping raw data will be reviewed centrally at The Ohio State University's Flow Cytometry Clinical Lab.

### 5.8.2 Cytogenetics with karyotyping and AML FISH panel

5.8.2.1 Specimen(s) Receipt and Processing at Ohio State University's Leukemia Tissue Bank

5.8.2.2 Site(s) Performing Correlative Study

This exploratory biomarker will be performed at locally and the chromosome pictures will be sent for central review at The Ohio State University's Cytogenetics Clinical Lab.

### 5.8.3 Next generation sequencing AML mutational analysis with Variant Allele Frequency

5.8.3.1 Specimen(s) Receipt and Processing at Ohio State University's Leukemia Tissue Bank

5.8.3.2 Site(s) Performing Correlative Study

This exploratory biomarker will be performed at The Ohio State University's Experimental Hematology Lab.

### 5.8.4 Tetramer analysis and Cytokine Production up re-stimulation with antigen peptide

5.8.4.1 Specimen(s) Receipt and Processing at The Ohio State University's Leukemia Tissue Bank

5.8.4.2 Site(s) Performing Correlative Study

This exploratory biomarker will be performed at The Ohio State University's Experimental Hematology Lab.

### 5.8.5 Global and gene-specific DNA methylation

5.8.5.1 Specimen(s) Receipt and Processing at The Ohio State University's Leukemia Tissue Bank

5.8.5.2 Site(s) Performing Correlative Study

This exploratory biomarker will be performed at The Ohio State University's Experimental Hematology Lab.

### 5.8.6 Venetoclax, OATP1B1 biomarker and nivolumab PK studies

5.8.6.1 Specimen(s) Receipt and Processing at The Ohio State University's PharmacoAnalytical Shared Resource

## 5.8.6.2 Site(s) Performing Correlative Study

This exploratory biomarker will be performed at The Ohio State University for the ChOP-KC.

## 6. TREATMENT PLAN

### 6.1 Agent Administration

Treatment will be administered as either an outpatient or inpatient basis as appropriate. Reported adverse events and potential risks are described in Section 10. Appropriate dose modifications are described in Section 7. No investigational or commercial agents or therapies other than those described below may be administered with the intent to treat the patient's malignancy.

Dose Scheduling			
Dose level	Venetoclax*	Decitabine	Nivolumab
Dose level -2	Cycle 1 Day 1 100mg Cycle 1 Day 2 200mg Cycle 1 Day 3-14 400mg  Cycle 2 and beyond Day 1-14 400mg	Induction 20 mg/m  intravenously on Days 1-10  Maintenance 20 mg/m  intravenously on Days 1-5	Flat dose of 240mg every 2 weeks starting on Day 15 of Cycle 1 and continue Day 1 and 15 with cycle 2 and subsequent cycles
Dose level -1	Cycle 1 Day 1 100mg Cycle 1 Day 2 200mg Cycle 1 Day 3-21 400mg  Cycle 2 and beyond Day 1-21 400mg		
Dose level 1	Cycle 1 Day 1 100mg Cycle 1 Day 2 200mg Cycle 1 Day 3-28 400mg  Cycle 2 and Cycle 3 (if needed) Day 1-28 400 mg  Maintenance cycles Day 1-21 400 mg		

### Regimen Description

Agent	Premedications; Precautions	Dose	Route	Schedule	Cycle Length
Nivolumab	Take precaution for infusion/anaphylactic reaction	240mg in max of 160ml NS	IV over 30 minutes	Days 1 and 15 (day 15 only for cycle 1)	
Decitabine	Premedicate with ondansetron 30 minutes prior to chemotherapy	20 mg/m  in 150ml NS	IV over 60 minutes	Days 1-10 for induction cycles and Days 1-5 for maintenance cycles	28 days (4 weeks)
Venetoclax*	Take with a meal and water. Premedicate with allopurinol and adequate hydration.	Four 100 mg tablets	PO in the a.m.	Daily, days 1-28 (with ramp up for cycle 1 only – Day 1 100mg, Day 2, 200mg, and Day 3 400mg) [note: days 1-21 for maintenance cycles]	

\*Please see Section 6.4.1.1 for dose adjustments with concurrent CYP3A inhibitor use

## 6.2 Order of administration

When infusions of nivolumab and decitabine are administered on the same day, nivolumab should be administered first, followed by decitabine. There should be 30 minutes of time between infusions.

### 6.2.1 Other Agent(s)

#### 6.2.1.1 Nivolumab

No specific premedications are required, but diphenhydramine, hydrocortisone, and epinephrine should be available in case of an infusion reaction or anaphylactic reaction. There are no known issues with intravenous solutions.

#### 6.2.1.2 Decitabine

Premedicate with 8 mg oral ondansetron 30 minutes prior to chemotherapy. There are no known issues with intravenous solutions.

#### 6.2.1.3 Venetoclax

Provide anti-hyperuricemic agents (allopurinol 300 mg daily, begin at least 72 hours prior to starting treatment with venetoclax) and adequate hydration to all patients prior to first dose and continue through ramp-up phase. Patients should be instructed to drink 6 to 8 glasses water each day, starting 2 days before the first dose, on the day of the first dose of venetoclax, and each time the dose is increased.

Tablets should be taken orally once daily, at approximately the same time, with a meal and water. Do not chew, crush, or break tablets.

If a dose is missed by less than 8 hours, take the missed dose right away and take the next dose as usual. If a dose is missed by more than 8 hours, the patient should wait and take the next dose at the usual time.

Patients should not take an additional dose if they vomit after taking venetoclax.

They should take the next dose at the usual time the following day.

Tell the patient to Avoid grapefruit products, Seville oranges, and starfruit during treatment.

### 6.3 Definition of Dose-Limiting Toxicity

The dose limiting toxicity period (DLT) will be defined as the time period from the start of nivolumab therapy on C1D15 to the end of cycle 3. DLT will be defined as non-hematologic toxicity of  $\geq$  grade 3 with the exception of grade 3 nausea and vomiting that resolves to  $<$  grade 3 within 72 hours, and infection (infection-related toxicities such as fever/sepsis, see below). The grade 3/4 toxicity, designated to be DLT, should be considered drug-related. Patients with transient grade  $\geq$  3 electrolyte abnormalities that are not clinically significant and are correctable within 24 hours will not be considered a DLT. Patients with  $\geq$  grade 3 transient liver function test abnormalities (AST, ALT, or alkaline phosphatase) that resolve to  $<$  grade 2 within 5 days will not be considered DLT only if it is self-limited without steroid treatment. Grade 3 or 4 infection will not constitute DLT unless it is felt that the infection resulted from unexpectedly complicated myelosuppression (degree or duration).

Hematological DLT will be considered as failure to recover neutrophil count (ANC $\geq$ 500), or platelet count  $\geq$ 25,000, or hemoglobin  $\geq$ 7 by Day 42 in patients with  $<$ 5% blasts in the bone marrow, absence of myelodysplastic changes, and/or absence of evidence of disease by flow cytometry in the bone marrow. For patients with  $\geq$  5% blasts, myelodysplastic changes, or evidence of disease by flow cytometry/cytogenetics, failure to recover neutrophil, platelet count, or hemoglobin may not be considered DLT as this could be the result of persistent disease.

Specifically with nivolumab, any patient who requires high dose steroids (any dose greater than the equivalent to 20 mg prednisone daily) will be considered to have experienced a DLT and will be taken off nivolumab but allowed to remain on decitabine and venetoclax.

Management and dose modifications associated with the above adverse events are outlined in Section 7.

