absence of active autoimmune disease. Patients are permitted to use topical, ocular, intra-articular, intranasal, and inhalational corticosteroids (with minimal systemic absorption). Physiologic replacement doses of systemic corticosteroids are permitted, even if  $\leq 10$  mg/day prednisone equivalents. A brief course of corticosteroids for prophylaxis (e.g., contrast dye allergy) or for treatment of non-autoimmune conditions (e.g., delayed-type hypersensitivity reaction caused by contact allergen) is permitted.

- 3.2.6 Patients with hyperleukocytosis requiring immediate cytoreductive chemotherapy (WBC  $\geq 100,000$  with symptoms of leukostasis)
- 3.2.7 Isolated extramedullary leukemia of CNS involvement with leukemia
- 3.2.8 Patients who have not recovered from adverse events due to prior anti-cancer therapy (i.e., have residual toxicities  $>$  Grade 1) with the exception of alopecia.
- 3.2.9 Patients who are receiving any other investigational agents.
- 3.2.10 History of allergic reactions attributed to compounds of similar chemical or biologic composition to decitabine, venetoclax, or nivolumab
- 3.2.11 Patients with uncontrolled intercurrent illness.
- 3.2.12 Patients with psychiatric illness/social situations that would limit compliance with study requirements.
- 3.2.13 Pregnant women are excluded from this study because fetal risk has been demonstrated with decitabine with the potential for teratogenic or abortifacient effects. Because there is an unknown but potential risk for adverse events in nursing infants secondary to treatment of the mother with decitabine, breastfeeding should be discontinued if the mother is treated with decitabine. These potential risks may also apply to other agents used in this study.

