
*Including CHF, LV systolic dysfunction, Myocarditis, CPK, and troponin
 
**Patients with evidence of myositis without myocarditis may be treated according as “other event”
 
Note: The optimal treatment regimen for immune mediated myocarditis has not been established. Since this toxicity has caused patient deaths, an aggressive approach is recommended.
	

All Other Events	Management/Next Dose for Nivolumab
$\leq$ Grade 1	No change in dose.
Grade 2	Hold until $\leq$ Grade 1 OR baseline (exceptions as noted below).
Grade 3	Hold until $\leq$ Grade 1 OR baseline and patient no longer on steroid treatment if initiated (exceptions as noted below). Permanently discontinue for events with a high likelihood of morbidity or mortality with recurrent events.
Grade 4	Off protocol therapy.
Recommended management: As clinically indicated	

- Any Grade 2 drug-related uveitis or eye pain or blurred vision that does not respond to topical therapy and does not improve to Grade 1 severity within the re-treatment period OR requires systemic treatment should go off protocol treatment
- Any Grade 3 or 4 drug-related laboratory abnormality or electrolyte abnormality, that can be managed independently from underlying organ pathology with electrolyte replacement, hormone replacement, insulin or that does not require treatment **does not** require discontinuation.
- Any AE, laboratory abnormality, or intercurrent illness which, in the judgment of the investigator, presents a substantial clinical risk to the subject with continued study drug dosing should go off protocol treatment.

Skin Rash and Oral Lesions	Management/Next Dose for Nivolumab
≤ Grade 1	No change in dose*.
Grade 2	Hold* until 1≤ Grade resolved. Resume at same dose level.
Grade 3	Hold* until ≤ Grade 1. Resume at same level at investigator discretion
Grade 4	Off protocol therapy.

\*Patients with purpuric or bullous lesions must be evaluated for vasculitis, Steven-Johnson syndrome, toxic epidermal necrolysis (TEN), and autoimmune bullous disease including oral lesions of bullous pemphigus/pemphigoid. Pruritus may occur with or without skin rash and should be treated symptomatically if there is no associated liver or GI toxicity. Note skin rash typically occurs early and may be followed by additional events particularly during steroids tapering.

Recommended management: AE management guidelines

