≤ Grade 1	No change in dose.
Grade 2	Hold pending evaluation for gastritis, duodenitis, and other immune AEs or other causes. Resume at same dose level after resolution to ≤ Grade 1.
Grade 3	Hold pending evaluation until ≤ Grade 1. Resume at same dose level. If symptoms do not resolve within 7 days with symptomatic treatment, patients should go off protocol therapy.
Grade 4	Off protocol therapy
Patients with Grade 2 or 3 N-V should be evaluated for upper GI inflammation and other immune related events.	

Fatigue	Management/Next Dose for Nivolumab
Grade 2	No change in dose.
Grade 3	Hold until $\leq$ Grade 2. Resume at same dose level.
Grade 4	Off protocol therapy.
Fatigue is the most common AE associated with immune checkpoint therapy. Grade 2 or greater fatigue should be evaluated for associated or underlying organ involvement including pituitary, thyroid, and hepatic, or muscle (CPK) inflammation.	

Neurologic events	Management/Next Dose for Nivolumab
$\leq$ Grade 1	Hold dose pending evaluation and observation. Resume with no change in dose when resolved to baseline.
Grade 2	Hold dose pending evaluation and observation. Hold until $\leq$ Grade 1. Off protocol therapy if treatment with steroids is required. Resume at same dose level for peripheral isolated n. VII (Bell's palsy).
Grade 3	Off protocol therapy.
Grade 4	Off protocol therapy
Patients with any CNS events including aseptic meningitis, encephalitis, symptomatic hypophysitis, or myopathy, peripheral demyelinating neuropathy, cranial neuropathy (other than peripheral n. VII), GB syndrome, and myasthenia gravis should be off study.	
Recommended management: See Neurologic AE Management Algorithm	

Endocrine Hypophysitis Adrenal Insufficiency	Management/Next Dose for Nivolumab
$\leq$ Grade 1	*Hold pending evaluation for evidence of adrenal insufficiency or hypophysitis. Asymptomatic thyroid stimulating hormone (TSH) elevation may continue treatment while evaluating the need for thyroid replacement.
Grade 2	Hold until patients are on a stable replacement hormone regimen. If treated with steroids, patients must be stable off steroids for 2 weeks. Resume at same dose level.
Grade 3	Hold until patients are on a stable replacement hormone regimen. If treated with steroids, patients must be stable off steroids for 2 weeks. Resume at same dose level.
Grade 4	Off protocol therapy.

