Prior to starting corticosteroids or hormone replacement for any reason, appropriate

endocrine testing including cortisol, Cortrosyn® adrenocorticotropic hormone (ACTH), thyroid stimulating hormone (TSH), and thyroxine (T4) must be obtained to document baseline.

Please note that in some cases the treatment algorithms recommend steroids if symptoms do not resolve in 7 days. However, this recommendation is not meant to delay steroid treatment at any time it is clinically indicated.

Any patient started on corticosteroids initially, who is determined to not require steroid treatment for an autoimmune AE, may resume therapy after a 2-week observation period without further symptoms at the discretion of the PI or investigator.

Any patient requiring high dose steroids (any dose greater than the equivalent to 20 mg prednisone) will be considered to have experienced a DLT and will be taken off nivolumab. These patients will be allowed to continue receiving decitabine and venetoclax on study.

Patients requiring high dose steroid treatment for autoimmune or inflammatory events should go off study treatment except for a short course of tapering steroids for infusion reaction, skin rash or endocrine events.

Patients with grade 3 thyroiditis and skin rash may continue therapy as for grade 2 events with resolution and stable replacement treatment.

Patients with thyroiditis or hypopituitarism who are stable as above may be restarted with replacement hormones including thyroid hormone and physiologic doses of corticosteroids.

Please note that grading and for hypophysitis with symptoms of headache, visual or neurologic changes or radiologic evidence of pituitary enlargement and other CNS events such as aseptic meningitis or encephalitis should be considered grade 3 events.

Patients may be dose-delayed for evaluation and restarted depending on results.

Any patient started on corticosteroids initially who is determined to not require steroid treatment for an autoimmune adverse event may resume therapy after a 2-week observation period without further symptoms at the discretion of the PI or investigator.

If doses of nivolumab are missed/delayed other than reasons for toxicity, they may be given +2 days of scheduled dose.

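### The steroid DLT criterion in Sections 6.3 and 7.5 has no attribution requirement and, as written, contradicts the Section 7.5 rules that let nivolumab continue or resume after high dose steroids

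*Combined protocol and SAP*

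**What the plan says.** Section 6.3 defines DLTs in separate paragraphs. For non-hematologic toxicity it adds a relatedness condition: "The grade 3/4 toxicity, designated to be DLT, should be considered drug-related". The steroid criterion comes later and stands alone: "Specifically with nivolumab, any patient who requires high dose steroids (any dose greater than the equivalent to 20 mg prednisone daily) will be considered" as having had a DLT and is taken off nivolumab, while decitabine and venetoclax may continue. Section 7.5 restates it: "Any patient requiring high dose steroids (any dose greater than the equivalent to 20 mg prednisone) will be considered to have experienced a DLT".

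Section 7.5 also contains rules under which nivolumab may go on after steroids:

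- **Suspected myocarditis, grade 2 or higher (cardiac table).** Nivolumab is held and high dose methylprednisolone is started. Treatment may resume on return to baseline if myocarditis is ruled out or thought unlikely.
- **Short tapers.** Patients needing high dose steroids for autoimmune or inflammatory events go off study treatment, "except for a short course of tapering steroids for infusion reaction, skin rash or endocrine events".
- **Steroids started but not needed.** A patient "who is determined to not require steroid treatment for an autoimmune AE, may resume therapy after a 2-week observation period".
- **Endocrine events, grades 2 and 3.** "If treated with steroids, patients must be stable off steroids for 2 weeks. Resume at same dose level".
- **All Other Events, grade 3.** Nivolumab is held until "Grade 1 OR baseline and patient no longer on steroid treatment if initiated".

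Section 7.6 speaks of a DLT attributed to nivolumab, but in a rule about continuing decitabine and venetoclax. It sets the steroid threshold at 20 mg or more, where Sections 6.3 and 7.5 use more than 20 mg. Section 9.1 accepts dose level 1 with at most 1 DLT in 6 patients.

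**The concern.** The MTD is the primary objective, and the DLT count is its only input. A criterion triggered by a drug dose alone can count a course given for a reason unrelated to nivolumab. It also removes nivolumab from patients whom another rule in the same section would allow back on it. A site that follows the sentence as written and a site that follows the Section 7.5 resumption rules could classify the same patient differently. The first could over-count. The second could leave out an event that the definition says to count.

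The observation window is long enough for this to arise. It runs from cycle 1 day 15 to the end of cycle 3, which is 14 + 28 + 28 = 70 days without delays. The classification also decides replacement, since Section 9.1 replaces patients who leave the window for reasons other than a DLT.

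**Working it through.** **Where the texts conflict.** The test is whether the other rule in Section 7.5 expressly involves high dose steroids.

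| Rule in Section 7.5 | High dose explicit? | Result against the steroid criterion |
|---|---|---|
| Suspected myocarditis, later excluded | Yes | Direct conflict: DLT and off nivolumab, yet may resume |
| Short taper for infusion reaction, rash or endocrine event | Yes | Direct conflict over stopping nivolumab; no express statement on DLT status |
| Steroids started, not needed for an autoimmune event | No dose given | Can be reconciled |
| Endocrine grades 2 and 3; All Other Events grade 3 | No dose given | Conflict only if the course exceeds 20 mg/day |

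The taper exception could be read as covering only decitabine and venetoclax. But the infusion reaction, skin and endocrine tables all allow nivolumab itself to resume at the same dose after grade 2 or 3 events, so that reading is hard to sustain.

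**The plan's own figures.** The protocol gives no operating characteristics for the 3+3. Its only error rates are for the expansion rule of 13 or more responses in 30. They reproduce: P(X ≥ 13 | 30, 0.30) = 0.0845 (stated 0.084) and P(X ≤ 12 | 30, 0.50) = 0.1808 (stated 0.181). They do not bear on this point.

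**Effect on dose level 1.** Dose level 1 is both the starting and the highest dose. Let t be the true DLT rate, which is assumed.

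Unrelated course not counted:

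P(reject) = 1 − [(1−t)^6 + 6t(1−t)^5]

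The sequential 3+3 with six patients required gives the same value: (1−t)^3[(1−t)^3 + 3t(1−t)^2] + 3t(1−t)^2(1−t)^3 = (1−t)^6 + 6t(1−t)^5.

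One of the six has an unrelated course that is counted, so any DLT among the other five rejects the dose:

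P(reject) = 1 − (1−t)^5

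| Assumed t | Not counted | One counted |
|---|---|---|
| 5% | 0.033 | 0.226 |
| 10% | 0.114 | 0.410 |
| 15% | 0.224 | 0.556 |
| 20% | 0.345 | 0.672 |

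For example, at t = 10%: 1 − (0.5314 + 0.3543) = 0.114, and 1 − 0.5905 = 0.410.

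**Averaged over how often it happens.** Let q be the assumed chance that a patient has an unrelated course above 20 mg in the window, independent of a true DLT. The counted rate is p = 1 − (1−t)(1−q), used in the first formula. At t = 10%:

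- q = 2%: p = 1 − 0.90 × 0.98 = 0.118, P(reject) = 0.151
- q = 5%: p = 1 − 0.90 × 0.95 = 0.145, P(reject) = 0.212

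The unconditional shift is therefore from 11% to between 15% and 21% over that range of q, and only if the criterion is always applied as written.

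**The case against.** The strongest reply is that the intended meaning is clear enough. The criterion opens with a reference to nivolumab, and Section 6.3 closes by referring to the items above it as adverse events. Section 7.5 is about nivolumab toxicity, and Section 7.6 speaks of attribution to nivolumab. This stands as evidence of intent. It does not put an attribution test into the definition, and it leaves the two direct conflicts in place, since both concern events managed as possible nivolumab toxicity.

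A second reply is that over-counting is cautious in a first test of this triplet, and that a false rejection costs little. That is largely right. In Section 6.1, dose level −1 shortens induction venetoclax from 28 to 21 days and leaves nivolumab, decitabine and the 21-day maintenance venetoclax unchanged. It also means that de-escalation would not address a steroid-triggering event caused by nivolumab.

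A third reply is that attribution brings judgement into an objective trigger, and Section 7.5 itself notes how hard inflammatory pneumonitis is to separate from infection. This is a fair cost, and the fix has to provide for it.

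Three stronger readings are tempting, and the documents do not support them:

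- A reader might infer that every resumption rule contradicts the criterion. The rule for steroids started but not needed can be reconciled, because the criterion applies to a patient who *requires* high dose steroids. The endocrine and All Other Events rows state no dose.
- A reader might take Section 3.2.5 as showing that unrelated courses are expected on treatment. It permits "A brief course of corticosteroids for prophylaxis (e.g., contrast dye allergy) or for treatment of non-autoimmune conditions", but as an eligibility rule, not a rule for the DLT window.
- A reader might conclude that dose level 1 is likely to be wrongly rejected. The 11% to 41% contrast is conditional on such a course having occurred and been counted. No frequency can be derived from the documents.

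**Conclusion.** The point holds as a conflict in wording that feeds the primary endpoint. The steroid criterion has no attribution requirement, and as written it contradicts Section 7.5 for suspected myocarditis that is excluded and for the excepted short tapers. One unrelated course counted as a DLT uses up the single DLT that dose level 1 is allowed. The probabilities rest on assumed values of t and q, independence between them, and application of the criterion as written. They show how sensitive a six-patient rule is and do not forecast this trial. The 20 mg mismatch in Section 7.6 matters only for a patient on exactly 20 mg. Since the likely intent is visible and a false rejection costs only venetoclax days, the severity is minor to moderate.

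**What to change.** 1. In Sections 6.3 and 7.5, count the steroid criterion only when more than 20 mg/day prednisone-equivalent is required within the DLT window for an adverse event considered at least possibly related to nivolumab. Include pneumonitis unless infection has been established as the cause.
2. Add that steroid courses for other reasons are not DLTs and that nivolumab may resume under Section 7.5, including after suspected myocarditis has been excluded.
3. State whether short tapers for infusion reaction, rash or endocrine events count as DLTs.
4. Change the Section 7.6 threshold to more than 20 mg.

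The cost is a clause in two sections, two sentences on handling and one changed symbol. The only real downside is one attribution judgement per steroid course. Section 6.3 already asks for that kind of judgement for grade 3/4 toxicity, and Section 10.2 already supplies the attribution scale. Setting the bar at possible relatedness, with the pneumonitis provision, keeps suspected immune toxicity in the count.
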